Aim 1: Test the impact of an intervention to target diffusion of responsibility with and without additional reduction in prescribing burden on SGLT-2i and GLP-1RAs prescribing compared to usual care. We will conduct a randomized trial among primary care providers. The primary outcome will be SGLT-2i and GLP-1RA prescribing for patients with poorly controlled type 2 diabetes and a clear indication for one of these medications.

[figure not shown]
Aim 2: Identify characteristics of the patient, provider, and their clinical interaction that are associated with responsiveness to each intervention using routinely collected EHR data. The effectiveness of these interventions may vary based on characteristics of patients, providers, or the clinical scenario. Identification of predictors of responsiveness will help target interventions to those most likely to benefit.

3. General Description of Study Design

This study will be conducted within MGH primary care. As with prior work, we will use the hospital's EHR database, the Epic Enterprise Data Warehouse, to identify patients. Patients will be eligible if they are: adults 18-84 years of age with poorly controlled type 2 diabetes (defined as HbA1c >7.0%) and a compelling indication for an SGLT-2i or GLP-1RA (including cardiovascular disease, kidney disease, heart failure, or obesity), who are not already prescribed one of these therapies. We will exclude individuals with end stage renal disease, dementia, type I diabetes, or an EHR indicator of hospice care. We will also exclude patients who are not on the MGH diabetes registry, because patients who are excluded from the registry typically have a clinical reason for alternative diabetes goals or care plans. All attending MGH PCPs (excluding those involved in the design or delivery of the intervention) will be included in the trial. Eligible PCPs will be randomized to one of three arms: (1) intervention to address diffusion of responsibility, (2) intervention to address diffusion of responsibility plus additional simplification of the prescribing process, and (3) usual care. Providers randomized to arm 1, the intervention to address diffusion of responsibility will receive an email from a peer offering encouragement and support in

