After study completion, we will conduct an exploratory chart review of the visit notes from a random sample of patients in all three arms. Within each study arm, we will randomly sample visit notes from charts of 20 patients who were prescribed an SGLT-2i or a GLP1RA during the target visit (primary outcome occurred) and 20 patients who did not receive a prescription (primary outcome did not occur) to qualitatively explore the nature of the conversations that were documented at the visit. This will also include reviewing other encounter types in patients charts like telephone notes, patient gateway messaging, and other visits. This data collection will come from Epic chart review only. We will review the chart and summarize the nature of that conversation that was had around initiating SGLT-2is or GLP-1s, if one was documented. We will review the notes from the visit that was targeted by the intervention as well as subsequent notes in the chart as needed (such as telephone encounters, patient gateway encounters, and specialists visits notes) in order to understand if a medication was prescribed, and if not, then what the barriers were to starting. We will collect information on whether the patient filled the new prescription at the pharmacy, if available. This will include a total of 120 sampled charts, and the qualitative analyses will help us identify potential characteristics to extract from routine EHR data for Aim 2 and help understand remaining barriers to prescribing as well as potential mechanisms behind intervention effectiveness. Finally, we will also review the charts of all patients who received a prescription for a new medication to see what proportion of these prescriptions were actually filled by patients.

We will use the MGB standardized deployments of AI/ML services in MGB's secure cloud infrastructure, specifically the Azure OpenAI models as a tool to analyze qualitative data from the study and compare results from the LLM to those obtained by investigator analyses. Use of the LLM will permit faster analysis of large amounts of qualitative free-text data.

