6.2.2 Aim 2 Design

In Aim 2, we will identify characteristics of providers, patients, and their interactions, that are measurable in routinely collected EHR data, that are associated with intervention responsiveness. We will extract provider demographic and practice data, patient demographic and clinical information, and data on the patient-provider interaction. We will also pre-specify which of these characteristics may be related to diffusion of responsibility.

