9.1.2 Aim 2 Analysis Plan

For analyses, we will fit separate logistic and boosted regression models using sets of these predictors to evaluate the ability to predict responsiveness to each intervention, and we will incorporate classification

and regression trees where appropriate. Boosted regression is a machine learning method robust to multi-collinearity and overfitting. For each regression, we will use 10-fold cross-validation to compare C-statistics for the ability to predict intervention response and calculate a continuous net reclassification index to assess changes in predicted response with additional predictors.^{26,27}

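### Aim 2 does not separate tuning and model choice from performance estimation; a best model chosen and reported from the same 10 folds would have a C-statistic too high by roughly 0.00 to 0.05

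*Combined protocol and SAP*

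**What the plan says.** Section 9.1.2 (Aim 2 Analysis Plan) states that "we will fit separate logistic and boosted regression models using sets of these predictors to evaluate the ability to predict responsiveness to each intervention", and adds classification and regression trees where they suit. It describes boosting in one sentence: "Boosted regression is a machine learning method robust to multi-collinearity and overfitting". Evaluation is as follows: "For each regression, we will use 10-fold cross-validation to compare C-statistics for the ability to predict intervention response". A second measure will "calculate a continuous net reclassification index to assess changes in predicted response with additional predictors".

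The section gives no learning rate, tree depth, number of trees or stopping rule. It describes no nested loop, hold-out set or repeated split, and no rule for choosing among models or predictor sets.

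The predictor sets are not listed. Section 6.2.2 promises only this much in advance: "We will also pre-specify which of these characteristics may be related to diffusion of responsibility". Section 6.2.1 says of the chart review that "the qualitative analyses will help us identify potential characteristics to extract from routine EHR data for Aim 2". The stated use of the results, under Aim 2 in section 2, is this: "Identification of predictors of responsiveness will help target interventions to those most likely to benefit".

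**The concern.** Cross-validation corrects the optimism of one model whose settings were fixed beforehand. It does not correct the optimism that arises when several candidates are scored on the same folds, the highest score is kept, and that score is then quoted as performance. The maximum of several noisy estimates is biased upward. Boosting adds to this, because its number and depth of trees must be set somehow and the plan provides no place to set them other than those folds. The claim of robustness to overfitting makes it easy to overlook this step.

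A second issue is stability. With one random partition, the ordering of predictor sets depends partly on the split.

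At stake is the credibility of the Aim 2 results. If true signal is weak, a modest C-statistic could come from selection alone, and the set of characteristics put forward for targeting could change with the random seed. The problem arises even if all patients are independent.

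**Working it through.** **Figures in the documents.** No C-statistic, number of candidates or sample size is given for Aim 2, so there is no Aim 2 figure to reproduce. The only design calculation is the Aim 1 power statement in section 9.2, which supplies the inputs. For 30% against 41%, two-sided 5% (sidedness assumed) and 80% power, the usual two-proportion formula gives 296 per arm, or 314 with continuity correction. The design effect is 1 + (7 − 1) × 0.07 = 1.42. Then 3 × 314 × 1.42 = 1337.6 patients, and 1337.6 / 7 = 191.1 providers, which agrees with the stated 191.

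**Inputs taken from the documents.** Patients per arm: 1468 / 3 ≈ 489. Prescribing rate in an intervention arm: 30% + 11 points = 41%.

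**Inputs assumed.** The number and make-up of predictor sets, the boosting settings, the signal strength, and modelling within one arm. The plan states none of these, so a range is shown.

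**Quantity computed.** Optimism = (cross-validated C of the candidate that scores best on the folds) − (C of that same fitted candidate in a large set of new patients), averaged over simulated data sets.

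**Designs.** For 2, 6 and 9 candidates: logistic regression and stump boosting on 10, 20 or 30 predictors, with a second boosting length in the 9-candidate case; 250 data sets; 20,000 new patients. For 33 candidates: 3 logistic, 6 tree and 24 boosted models on three sets drawn from 24 predictors; 25 data sets; 6,000 new patients.

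| Candidates | No signal: reported / true | Moderate signal: reported / true | Strong signal: reported / true |
|---|---|---|---|
| 2 | 0.5154 / 0.5001 (+0.015) | 0.5945 / 0.5941 (+0.000) | 0.6786 / 0.6731 (+0.006) |
| 6 | 0.5351 / 0.4997 (+0.035) | 0.6179 / 0.6013 (+0.017) | 0.7212 / 0.7153 (+0.006) |
| 9 | 0.5382 / 0.4999 (+0.038) | 0.6189 / 0.5996 (+0.019) | 0.7213 / 0.7145 (+0.007) |
| 33 | 0.545 / 0.499 (+0.046) | 0.603 / 0.576 (+0.027) | not run |

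The Monte Carlo standard error is about 0.002 in the first three rows and 0.006 in the last. The last row's signal was somewhat weaker than the moderate signal above it. A separate 9-candidate run gave +0.038 with no signal and +0.024 with modest signal.

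**A model fixed in advance.** With no signal, the mean cross-validated C of each single model was 0.502 to 0.505 against a true 0.500. Across all scenarios it stayed within about 0.01 of the truth.

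**Does boosting overfit here?** Yes. With no signal, the C of stump boosting on its own training data averaged 0.65 to 0.76, against 0.58 to 0.64 for logistic regression. Cross-validation exposes this for a fixed model.

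**Does nesting remove the optimism?** With 6 candidates and 80 data sets, the single-loop, nested and true values were 0.534, 0.502 and 0.501 with no signal, and 0.622, 0.602 and 0.599 with moderate signal. The nested bias is within Monte Carlo error (about 0.004).

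**Stability.** In the 33-candidate design, a second random split of the same data chose the same model in 5 of 25 data sets (no signal) and 14 of 25 (signal). In the separate 9-candidate run the shares were 40% and 65%. The split alone gave the C difference between two logistic predictor sets an SD of about 0.011. Averaging over 50 random splits would reduce that part to 0.011 / √50 ≈ 0.0016.

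**The case against.** A reader might infer that Aim 2 will report a C-statistic that is too high. The documents do not support that. Section 9.1.2 says that C-statistics will be compared, but names no winner, no selection rule and no headline value. The reclassification index suits a comparison with and without added predictors as well as it suits a search for the best model. If every model is fixed beforehand and reported, each C is nearly unbiased. Even when a winner is reported, the bias is an average: with 6 candidates the winner's C was at or below its true value in 12% of data sets with no signal, 29% with moderate signal and 41% with strong signal.

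A reader might also infer that the robustness sentence itself distorts the results. It does not, since every regression is cross-validated whatever that sentence says. Nor does the section say that only one partition will be used or that tuning will happen outside the training folds; it is silent on both.

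The size of the effect rests on an assumed search. A grid of 33 candidates appears nowhere in the documents, and low agreement between splits is to be expected when there is no signal to find. More dramatic results from one arbitrary model (100 trees of depth 3: C of 0.999 on its own noise data against 0.499 in new data, and a calibration slope of about 0.2 with signal) describe that choice of settings rather than the plan.

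All of this stands, and it makes the point conditional. What remains is that a plan to compare several model types and predictor sets, with targeting in view, invites a choice, and the section does not say how that choice would be kept apart from the estimate of performance.

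**Conclusion.** The point holds in conditional form. Section 9.1.2 overstates the robustness of boosting and describes plain 10-fold cross-validation, with no separation of tuning or model choice from performance estimation. If the best of several models is tuned or chosen and reported from the same folds, the expected optimism in its C-statistic is roughly 0.00 to 0.05. It is largest with weak signal and many candidates, and near zero with strong signal or few candidates. If a single partition is used, the ranking of predictor sets also carries split noise with an SD of about 0.01.

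These sizes assume one arm of about 489 patients, 41% events, independent patients and 2 to 33 candidates. Modelling an intervention arm together with usual care would use more data and should reduce them. Aim 1 is unaffected. This is an inexpensive improvement to a secondary predictive aim.

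**What to change.** In section 9.1.2, replace the plain 10-fold cross-validation with repeated, nested 10-fold cross-validation (for example 50 random partitions). Make all tuning, and any choice of model type or predictor set, inside the training folds. Take the C-statistic and the net reclassification index from the outer folds, averaged over repeats. If no model is to be chosen, say so, fix the models and their settings in advance, and report the repeated cross-validated C of every one.

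Delete the claim of robustness to overfitting; that deletion alone changes no result. A held-out calibration slope beside the C-statistic is an optional addition.

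The cost is a few sentences, more computing time and a slightly lower reported C-statistic. Two limits apply. Repeating the split removes partition noise, not sampling variation: the SD of a cross-validated C between data sets was about 0.03 to 0.04. Nesting also does not remove leakage if one provider's patients are spread across folds, which is a separate point.

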9.2 Power Analysis

We estimate that 191 providers caring for 1468 eligible patients will provide 80% power to observe an 11 percentage-point difference in prescribing rates between each intervention arm and control, assuming a control arm prescribing rate of 30%, an ICC of 0.07, an average of 7 patients per provider, and a type I error rate of 5%.

10. Monitoring and Quality Assurance

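### Aim 2's 10-fold cross-validation does not require a PCP's patients to stay in one fold; with patient-level folds, provider predictors with no true effect can look predictive

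*Combined protocol and SAP*

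**What the plan says.** Section 9.1.2 gives the models: "we will fit separate logistic and boosted regression models using sets of these predictors", with classification trees added where suitable. For validation, "we will use 10-fold cross-validation to compare C-statistics for the ability to predict intervention response", together with a continuous net reclassification index for added predictors. It also states: "Boosted regression is a machine learning method robust to multi-collinearity and overfitting". The section names neither the unit that is assigned to folds nor any allowance for clustering.

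Section 6.2.2 describes the predictors: "We will extract provider demographic and practice data, patient demographic and clinical information, and data on the patient-provider interaction". The first group takes the same value for every patient of a PCP.

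Elsewhere the plan treats patients as clustered. Section 5.2 randomizes providers, section 9.1.1 uses generalized estimating equations for Aim 1, and section 9.2 assumes "an ICC of 0.07, an average of 7 patients per provider". Aim 2 has no counterpart to these provisions.

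**The concern.** Cross-validation gives an honest C-statistic only if the test fold is independent of the training folds. With folds drawn by patient, a PCP's patients are spread over the folds. Provider variables, alone or in combination, can then act as a label for the PCP, and the model carries that PCP's prescribing rate from the training patients to the test patients. The test fold rewards this even when the provider variable has no relation to prescribing. Resistance of the learner to overfitting does not help, because the fault lies in how the test data are separated.

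Section 2 says that Aim 2 is meant to identify patient, provider and interaction characteristics that help to target the interventions. A leak of this kind gives credit to provider variables that have earned none. It does so more for boosting and trees than for logistic regression, so the comparison of predictor sets and the comparison of models would both be distorted.

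**Working it through.** **Inputs from the documents.** 191 providers and 1468 patients (9.2), so 1468/191 = 7.69 patients per PCP. Three equal arms (5.2), so 191/3 ≈ 64 PCPs and 1468/3 ≈ 489 patients per arm. Control rate 0.30 and difference 0.11 (9.2), so 0.41 in an intervention arm. ICC 0.07 (9.2).

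**The plan's own figure.** The documents give no number for Aim 2, but the clustering inputs can be checked against the stated power. For 0.30 v 0.41, two-sided 5% and 80% power, the continuity-corrected size is 314 per arm. The design effect is 1 + (7 − 1) × 0.07 = 1.42. Then 314 × 1.42 × 3 = 1338, and 191 × 7 = 1337. The 80% is reproduced, so ICC 0.07 is a working assumption of the plan. (The 1468 patients imply 7.69 per PCP, not 7; this does not affect the present point.)

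**How often a PCP is split.** With patients assigned to 10 folds at random, the chance that all 6 other patients of a 7-patient PCP fall in the same fold as a given patient is 0.1^6, one in a million. On average (7.69 − 1) × 0.9 ≈ 6 of a test patient's fellow patients are in the training data.

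**What recognising the PCP is worth.** Let X be the observed rate among m = 6 training patients of the same PCP. The mean of X differs between prescribed and non-prescribed test patients by the ICC, 0.07. The SD of X is √[0.41 × 0.59 × (1 + 5 × 0.07)/6] = √(0.2419 × 1.35/6) = 0.233. Under a normal approximation, C ≈ Φ(0.07/(0.233 × √2)) = Φ(0.212) = 0.584. A model that does nothing except identify the PCP therefore scores about 0.58. The same formula gives 0.50 at ICC 0, 0.527 at ICC 0.02 and 0.655 at ICC 0.15.

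**Simulation.** One arm of 64 PCPs, beta-binomial outcomes, rate 0.41, ICC 0.07, all predictors pure noise. Boosting used 100 trees, depth 3, rate 0.1; single trees had a minimum leaf of 5; logistic models were unpenalised. Continuous sets used 100 data sets each (Monte Carlo SE about 0.004); categorical sets used 35 to 60 (SE up to 0.007). Mean C-statistic, patient folds v PCP folds:

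| Null predictors | Boosted | Single tree | Logistic |
|---|---|---|---|
| 10 continuous provider | 0.586 v 0.495 | 0.586 v 0.503 | 0.537 v 0.506 |
| 5 continuous provider | 0.587 v 0.501 | 0.585 v 0.503 | 0.529 v 0.504 |
| 1 continuous provider | 0.586 v 0.498 | 0.584 v 0.503 | 0.514 v 0.506 |
| 4 categorical provider (2–4 levels), separate runs | 0.546 to 0.558 v 0.481 to 0.497 | – | 0.529 v 0.507 |
| 2 categorical provider | 0.524 v 0.500 | – | – |
| 1 binary provider | 0.509 v 0.500 | – | – |
| 5 continuous provider + 10 patient | 0.535 v 0.506 | 0.517 v 0.499 | 0.515 v 0.500 |
| 4 categorical provider + 10 patient | 0.502 v 0.501 | – | – |

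The highest boosted value in any run at ICC 0.07 was 0.598 (continuous predictors; 0.499 with PCP folds). With 10 continuous predictors, boosted values under patient folds were 0.499, 0.531 and 0.659 at ICC 0, 0.02 and 0.15, close to the formula. The effect vanishes without clustering, which identifies the cause.

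**Gain from adding null provider predictors to patient predictors (boosted).** Six added to five patient predictors, three of them real: mean +0.038, with a rise in 90 of 100 simulated arms, against +0.002 and 49 of 100 with PCP folds. A separate run gave +0.033 for continuous variables and +0.005, within Monte Carlo error, for coarse categorical ones.

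**Comparison of learners.** With 10 continuous null predictors, boosting appears to beat logistic regression by 0.586 − 0.537 = 0.049 under patient folds. Under PCP folds the difference is 0.495 − 0.506 = −0.011.

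**The case against.** The strongest reply is that the plan is silent, not wrong. Section 9.1.2 does not say that folds are formed from patients, and a team that uses generalized estimating equations and an ICC in Aim 1 may well intend to group folds. That stands: a reader might infer that the plan prescribes patient-level folds, and the text does not support this. What remains is that nothing in the plan prevents the default, under which the comparison goes wrong.

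The size is also uncertain. Provider demographic and practice data are often coarse categories shared by many PCPs, and the documents list no variables. With few such categories, or among many patient predictors, the leak is small or undetectable, and for logistic models it is small throughout. So 0.58 to 0.60 should not be read as the expected error in the reported C-statistics.

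A reader might also infer that the models are meant for PCPs outside the data. Sections 1 and 2 speak only of tailoring and targeting. For new patients of the same PCPs, past prescribing by that PCP is legitimate information and patient-level folds answer a relevant question. Even then, a gain that comes from recognising the PCP should not be credited to a provider characteristic, and identifying characteristics is the stated purpose of Aim 2.

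Finally, the sentence on boosting is a general remark whose removal would change no analysis, and the plan proposes no intervals for C-statistic differences. Neither needs a change here.

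**Conclusion.** The point holds as an unspecified fold unit with a predictable bias if the default is used. At the plan's own ICC and one arm of about 64 PCPs, null provider predictors alone score about 0.52 to 0.60 with boosted trees (a single binary variable, at 0.509, is the exception) and about 0.51 to 0.54 with logistic models. PCP folds give about 0.50. The gain from adding them to patient predictors runs from negligible to about +0.03 to +0.04. The direction is consistent: towards provider variables and towards flexible learners.

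These sizes rest on assumptions that the documents do not give: the number and coding of predictors, the tuning, the spread of panel sizes, and responsiveness modelled as prescribing within an arm. The net reclassification index was not simulated. The Aim 1 comparison and its power are unaffected.

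**What to change.** State in section 9.1.2 that cross-validation folds are formed by PCP, so that all patients of a PCP fall in the same fold; that any tuning is done inside the training folds under the same grouping; and that the C-statistic and the net reclassification index are computed from those out-of-fold predictions. If prediction for new patients of the same PCPs is also of interest, report patient-level folds as a separately labelled secondary result. Settle this before any C-statistic has been seen.

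The cost is a sentence and a grouping option in the software, with no new data. C-statistics will be somewhat lower and will vary slightly more from fold to fold.
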